8.3 Covariates and Subgroups

(ICH E3; 9.7.1, 11.4.2.1. ICH E9; 5.7)

As mentioned above, patients will be randomized. This will remove the effect of possible confounders.

The randomization and treatment allocation will be stratified by center. We will use alternating blocks of 4 and 6 patients which will lead to a maximum imbalance of 3 participants per center. We consider this to be an acceptable amount of imbalance.

At this moment we do not have the intention to analyze subgroups. We do not exclude the possibility of exploratory subgroup analysis but these results can only be presented as summary statistics.

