#### 8.1.3 Other study parameters (if applicable)

Demographics

Vital signs

Sputum for routine bacterial cultures

Serum sample for storage at -80 degrees Celsius

Sputum sample for storage at -80 degrees Celsius

Charlson Comorbidity Index

---

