In international literature there is scarce information about the percentages of treatment failure in patients admitted with an AECOPD receiving usual care. Therefore, we have performed a further search on PCT studies with a primary outcome of 30-day treatment failure. In the study by Schuetz et al. [6], who studied patients with lower respiratory tract infection, 30-day treatment failure was observed in 15.5% of the patients randomised to biomarker-based treatment, as compared to 18.9% in those randomised to usual care. This implies a relative risk of 0.82 in favour of the biomarker-based strategy. The study by Schuetz et al. was designed as a non-inferiority study, using a non-inferiority boundary of 7.5%. In view of these data we decided to design our study as a non-inferior study, whereas we choose a non-inferiority boundary of 5.0%. We based the primary outcome on the study of Huang et al. [13]. The incidence of the primary outcome was 20.4%. Using the relative risk of 0.82 in favour of the PCT-guided treatment group we expect the incidence of the primary outcome to be 16.7% in the PCT-guided treatment group. Then a total sample size of 626 is required (313 per treatment arm) to demonstrate non-inferiority with a power of 80%, and applying a one-sided alpha error of 0.025. We aim to enroll a total of 690 patients, accounting for a 10% drop-out rate.

8 General Analysis Considerations

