8.5.5 Adjustment of Confidence Intervals and p-values

An interim analysis will be performed after 50% of the participants needed has been accrued/included. The analysis will focus on the primary outcome and on safety. The non-inferiority design of the study means that a clear disadvantage of the PCT-guided treatment arm or in other words a clear benefit of the usual care arm will lead to discontinuation of the trial. The p-value at the interim analysis will be 0.0054 according to the O'Brien-Fleming method, and the p-value at final analysis will be 0.0492 [14]. The safety data consists of observed adverse events and SAE. The safety data consists of observed adverse events and SAE. The change of the p-value at final analysis will lead to an increase of 2 patients per treatment arm. The number of patients per treatment arm will be 315. Using a 10% drop-out rate this will lead to a total number of patients of 693.

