8.6 Multiple Testing

Op dit moment niet van toepassing, mogelijk nog wanneer primair eindpunt zou veranderen.

9 Summary of Study Data

Table 1. Baseline characteristics

The baseline characteristics are given in the table below.

	Usual care (n = 308)	PCT-guided treatment (n = 308)
Age in years – mean±SD		
Male gender – no. (%)		
BMI – mean±SD		
Smoking status: - current – no. (%) - past – no. (%) - pack years (mean, range)		
FEV1 % predicted - mean±SD		
GOLD classification: - I – no. (%) - II – no. (%) - III – no. (%) - IV – no. (%)		
Exacerbation type: - type I – no. (%) - type II – no. (%) - type III – no. (%)		
Median duration of symptoms in days - mean±SD		
CRP in mg/L – median [IQR]		
WBC 10 ⁹ /L – mean±SD		
CAT score – median [IQR]		
EXACT- RS score – median [IQR]		

Primary outcome

The primary outcome will be treatment failure within 30 days. A non-inferiority margin of 5% will be used to assess non-inferiority. Treatment failure is defined as disease-related mortality, endotracheal intubation, vasopressors, renal failure, lung abscess/empyema, development of pneumonia and hospital readmission within 30 days.

- Binary outcome parameter: yes or no. Description: number and percentage.
- To account for the multicenter effect a logistic mixed effects model will be estimated with

centers as random effect and treatment group as fixed effect to analyze the primary outcome. The risk of primary endpoint in the PCT guided treatment arm versus the usual care treatment arm will be reported with an odds ratio from the logistic model, with a 95% confidence interval. Based on this CI we will determine non-inferiority of the treatment.

Secondary outcome parameters

Skewed data will be analyzed using non-parametric tests. Paired measurements will be analyzed using paired tests.

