10.2 Secondary Efficacy Analyses

10.2.1 Secondary Analyses of Primary Efficacy Endpoint

Our primary analysis population will be the per-protocol population because of the non-inferiority design. The secondary analysis population will be the intention-to-treat analysis.

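### SAP 8.3's appeal to randomisation does not cover the per-protocol set that decides non-inferiority, and the primary model adjusts for centre only

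*SAP*

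**What the plan says.** SAP 8.3, the section on covariates, names no baseline covariate. It notes that patients are randomised and adds: "This will remove the effect of possible confounders". SAP 8.3.1 adds random centre effects. SAP section 9 (Primary outcome) specifies a logistic mixed model with "centers as random effect and treatment group as fixed effect to analyze the primary outcome", and SAP 10.1 bases the non-inferiority decision on the odds ratio from that model. The protocol's primary analysis (section 10) is instead a risk difference compared with a 5-point margin, also without covariates.

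On the analysis set, SAP 10.2.1 states: "Our primary analysis population will be the per-protocol population because of the non-inferiority design". ITT is secondary. SAP 8.2.2 makes PP membership depend on meeting the eligibility criteria, on sufficient compliance with treatment over at least 5 days, and on having no serious deviation. SAP 9.3 excludes from PP a patient with low PCT who is nevertheless prescribed antibiotics, and itself says that this could affect the primary endpoint.

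Baseline variables in the SAP Table 1 shell include age, FEV1 % predicted, GOLD class, exacerbation type, CRP, white cell count, CAT and EXACT-RS. Protocol 8.1.3 also lists the "Charlson Comorbidity Index". PCT is measured in both arms (Protocol sections 3 and 8.3).

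**The concern.** Randomisation balances the groups as allocated, in expectation. It gives no such assurance for a subset chosen afterwards, least of all when the choice works differently in the two arms. PCT results are withheld in usual care, where prescribing is the physician's choice, so overriding a low PCT can be a deviation only in the PCT-guided arm. If physicians override more often in patients who look sicker, the PP comparison loses higher-risk patients from one arm. The PCT strategy then looks better than it is, which in a non-inferiority trial is the dangerous direction.

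At stake are the error rate of the deciding analysis and, separately, some precision that recorded baseline data could supply.

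**Working it through.** **1. Reproduce the plan's sample size.** Inputs from SAP sections 7 and 8.5.5: failure 20.4% in usual care and 16.7% with PCT guidance, margin 5 points, 80% power, "applying a one-sided alpha error of 0.025", and after the interim "the p-value at final analysis will be 0.0492" (0.0492/2 = 0.0246 one-sided).

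- Variance sum: 0.204×0.796 + 0.167×0.833 = 0.3015
- Distance to the margin: 0.05 + 0.204 − 0.167 = 0.087
- n per arm = 0.3015 × (z₁₋α + z₀.₈)² / 0.087² = 312.6, so 313 at α = 0.025; 314.2, so 315 at α = 0.0246
- Power at 315 per arm = Φ(0.087/√(0.3015/315) − 1.967) = 80.1%

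The plan's 313 and 315 both reproduce.

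**2. Precision forgone.** The documents give no prognostic strength, so R² (share of outcome variance explained) is an assumption. On the risk-difference scale, the effective n is 315/(1 − R²) and the interval shrinks by 1 − √(1 − R²).

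| Assumed R² | Effective n per arm | Interval narrower by | Power |
|---|---|---|---|
| 3% | 325 | 1.5% | 81.3% |
| 5% | 332 | 2.5% | 82.1% |
| 10% | 350 | 5.1% | 84.1% |
| 15% | 371 | 7.8% | 86.1% |

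**3. How far one-sided PP exclusion could move the result.** Assume the true difference sits at the margin (25.4% v 20.4%). A fraction f of the PCT arm is removed, with failure risk r times that of patients kept. Risk among those kept = 0.254/(1 − f + f·r). Type I error = Φ((0.254 − kept risk)/SE − 1.967), with 315 in usual care and 315(1 − f) in the PCT arm. Nominal is 2.46%.

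| f | r | Kept risk | Shift (points) | Type I error |
|---|---|---|---|---|
| any | 1.0 | 25.4% | 0 | 2.46% |
| 5% | 1.5 | 24.8% | −0.6 | 3.7% |
| 10% | 1.5 | 24.2% | −1.2 | 5.4% |
| 10% | 2.0 | 23.1% | −2.3 | 10.0% |
| 20% | 2.0 | 21.2% | −4.2 | 23.2% |

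With r below 1 the shift reverses: f = 10%, r = 0.5 gives 0.254/0.95 = 26.7%, or +1.3 points.

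**4. How much adjustment recovers.** This was simulated with 3,000 runs per cell, 315 per arm and no centre effects. Exclusion in the PCT arm (f = 10%) was driven by one baseline score, with exclusion log-odds +1 per SD. Type I error:

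| Failure OR per SD | Unadjusted | Adjusted for the score | Adjusted for a proxy (correlation 0.5) |
|---|---|---|---|
| 1.25 | 3.5% | 2.9% | 3.0% |
| 1.5 | 4.2% | 3.0% | 4.0% |
| 2.0 | 5.9% | 2.8% | 4.8% |
| 2.5 | 7.7% | 3.1% | 5.2% |

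The Monte Carlo standard error near 2.5% is √(0.0246×0.9754/3000) = 0.3 points. With no exclusions, type I error was about 2.5% with or without adjustment, and adjusted power was about 81%, 82%, 84% and 86% across the four rows, against 80% to 81% unadjusted.

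**5. Scale.** Five points above 20.4% is an odds ratio of (0.254/0.746)/(0.204/0.796) = 1.33 at that control rate only. Adding covariates to a logistic model changes what its conditional odds ratio means, so the gain in step 2 applies to a standardised risk difference and not to the planned odds ratio.

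**The case against.** The strongest reply is that forgoing 2 to 4 points of power is a choice rather than an error, and that all bias figures depend on assumed exclusion rates and assumed risk differences. That stands: if excluded and retained patients carry the same risk, there is no bias. The SAP also analyses all efficacy variables in ITT, which mitigates the problem. However, ITT is secondary, its definition requires at least one dose, and no rule says both sets must support non-inferiority. The Table 2 specification in SAP section 17 foresees an adjusted estimate but names no covariates.

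Three stronger readings are tempting and are not supported:

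- **The recorded variables are strong predictors.** No passage links any of them to 30-day failure. FEV1 may be up to five years old (Protocol 4.2), and the Charlson index is in neither assessment schedule nor the SAP Table 1 shell.
- **Adjustment makes the PP analysis valid.** It does so only if the covariates explain exclusion. The documents do not say what drives an override, and the proxy column in step 4 shows what imperfect covariates leave behind.
- **SAP 8.3 gives randomisation as its reason for omitting covariates.** That is an inference from the section's title and content; the text does not draw the link.

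**Conclusion.** The point holds in a limited form. The sentence in SAP 8.3 is defensible for the all-randomised comparison and does not cover the PP set on which the conclusion rests. The PP selection rules are post-randomisation, and one of them is specific to one arm. The primary model includes nothing beyond centre that could offset this.

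The expected gain from adjustment is modest: power of about 82% to 84% instead of 80.1% for an assumed R² of 5% to 10% (81.3% to 86.1% for 3% to 15%), with 315 analysed per arm. The possible PP bias ranges from none to material across the scenarios shown. A reader might infer that the primary result will be biased, but the documents give neither an exclusion rate nor the risk of excluded patients, so they show only that the stated protection is absent. Adjustment would reduce that exposure without guaranteeing its removal. The change is worth making, and the plan is not invalid without it.

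**What to change.** - **SAP 8.3:** limit the sentence to the comparison of all randomised patients.
- **SAP 8.3, 9 and 10.1:** before database lock, prespecify one short list of pre-randomisation covariates, used identically in ITT and PP in addition to centre. Candidates are age, FEV1 % predicted, and acute-severity measures already collected, such as exacerbation type and CRP. Include the Charlson index only if it is confirmed as recorded at baseline.
- **Log PCT:** include it in both sets or in neither, and only if the sample is drawn before randomisation. Both schedules put sampling and randomisation at the same visit without giving the order.
- **Antibiotic pre-treatment:** Protocol 8.2 stratifies on it, whereas SAP 6.2 excludes such patients and SAP 6.1, 6.3 and 8.3 stratify by centre only. These passages must be reconciled before the factor enters the model.
- **Estimate:** obtain the adjusted arm difference in 30-day failure by standardisation and compare its confidence interval with the 5-point margin in Protocol section 10.
- **Interpretation:** state that adjustment may not remove PP selection bias, and keep the ITT analysis, with the same covariates, as an essential check on the PP conclusion.

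The cost is SAP wording and a few lines of code, with no new data collection. The small downside is that the covariate list, and a rule for missing covariate values, must be settled in advance.

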8.3.1 Multi-center Studies

(ICH E3;9.7.1, 11.4.2.4. ICH E9; 3.2)

We will adjust for center using random center-effects, this allows treatment effect to be different between centers. The combining of centers is necessary to be able to include the large number of patients needed according to our power analysis. Performing the same research in one center would lead to a much longer duration of the trial. The maximum number of patients recruited in one center in one year was estimated to be around 40, this would mean the trial would take up to more than 15 years before all of the 678 patients are included. The combining of centers also allows for testing the PCT-guided strategy in a variety of settings, and this will lead to a greater generalizability of the results.

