### 4.4 Sample size calculation

In international literature there is scarce information about the percentages of treatment failure in patients admitted with an AECOPD receiving usual care. Therefore, we have performed a further search on PCT studies with a primary outcome of 30-day treatment failure. In the study by Schuetz et al. (JAMA 2009), who studied patients with lower respiratory tract infection, 30-day treatment failure was observed in 15.5% of the patients randomised to biomarker-based treatment, as compared to 18.9% in those randomised to usual care. This implies a relative risk of 0.82 in favour of the biomarker-based strategy. The study by Schuetz et al. was designed as a non-inferiority study, using a non-inferiority boundary of 7.5%. In view of these data we decided to design our study as a non-inferior study, whereas we choose a non-inferiority boundary of 5.0%. We based the primary outcome on the study of Huang et al. (NEJM 2018) (15). The incidence of the primary outcome was 20.4%. Using the relative risk of 0.82 in favour of the PCT-guided treatment group we expect the incidence of the primary outcome to be 16.7% in the PCT-guided treatment group. Then a total sample size of 626 is required (313 per treatment arm) to demonstrate non-inferiority with a power of 80%, and applying a one-sided alpha error of 0.025. We aim to enroll a total of 690 patients, accounting for a 10% drop-out rate. Because of an interim-analysis this number of patients will increase to 693 (as detailed below in section 10.4).

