8.1 Timing of Analyses

Give details here of when, or under what criteria, the final analyses will be performed. Give details of what data cleaning and locking processes must take place to comply with standard operating procedure (SOP) specifications. For example:

- The final analysis will be performed when 693 subjects have completed the follow-up of 30 days, after which the database will be locked.

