The quality of life endpoints, using the COPD Assessment Test (CAT) and the EXACT-respiratory symptoms questionnaire, consist of multiple (three) measurements per subject. These measurements are all performed on the same time point (baseline, day 10 and day 30). These endpoints will be scored using the mean score and standard deviation when normally distributed and a median with the inter quartile range when the data have a skewed distribution. These data will be analyzed with a mixed effects model with random effects for center and patient to account for the extra hierarchical level in the data. The residuals will be evaluated for normality to test the assumptions of the models. In case of violations, transformations will be conducted on the dependent variable.

The unpaired continuous variables will be reported using the mean score and the standard deviation (normal distribution) or the median with the inter quartile range (skewed distribution). These variables will be analyzed using an mixed effects model.

The frequency and percentage will be reported for the categorical (mostly dichotomous) variables. Analysis of these variables will be performed using a logistic mixed-effects model.

- The analysis populations upon which the tables and figures will be based will be the per-protocol analysis population.

Table 2. Primary endpoint and secondary endpoints

	PCT-guided treatment (n = 315)	Usual care (n = 315)		p-value
Primary endpoint:				
Overall treatment failure:	n (%)	n (%)	OR (95% CI)	
- Disease-related mortality	n (%)	n (%)		
- Endotracheal intubation	n (%)	n (%)		
- Vasopressors	n (%)	n (%)		
- Renal failure	n (%)	n (%)		
- Lung abscess/empyema	n (%)	n (%)		
- Pneumonia development	n (%)	n (%)		
- Hospital readmission	n (%)	n (%)		
Secondary endpoints				
Incomplete resolution of the clinical signs and symptoms at day 30 after (scored using the modified Anthonisen criteria)	n (%)	n (%)	OR (95% CI)	

Change in QoL using the CAT: after 10 days after 30 days	mean (SD)or median [IQR]	mean (SD)or median [IQR]		
Start of antibiotic therapy after an initial opposite decision (after 48 hours)	n (%)	n (%)	OR (95% CI)	
Side effects (gastro-intestinal complaints, allergic reactions)	n (%)	n (%)	OR (95% CI)	
Cumulative antibiotic consumption	mean/median days (SD) or [IQR]	mean/median days (SD) or [IQR]		
Cumulative prednisolone consumption	mean/median days (SD) or [IQR]	mean/median days (SD) or [IQR]		

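### Three planned totals (678, 690 and 693) stand in the current text; 693 allows for 9.1% loss, not the stated 10%, and SAP 8.1 uses it as a count of completers

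*SAP*

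**What the plan says.** **Totals**

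- **678:** the protocol synopsis (number of subjects) and SAP 8.3.1, which estimates how long a single centre would need "before all of the 678 patients are included".
- **690:** SAP 7 says "We aim to enroll a total of 690 patients, accounting for a 10% drop-out rate" and stops there. SAP 9.1 repeats 690 as the four-year recruitment aim. Protocol 4.4 also gives 690, but its next sentence raises it to 693 because of the interim analysis.
- **693:** protocol 4.4, 10.4 and 11.2, and SAP 8.1 and 8.5.5. The derivation in SAP 8.5.5 is 315 per arm and then "Using a 10% drop-out rate this will lead to a total number of patients of 693".

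**Trigger.** SAP 8.1 states: "The final analysis will be performed when 693 subjects have completed the follow-up of 30 days". SAP 9.1 counts a subject as having completed the study when the day 10 and day 30 data are complete. Protocol 8.5 rules out replacement once the randomised quota has been reached.

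**Table shells.** In SAP 9, the Table 1 shell has 308 per arm and the Table 2 shell has 315 per arm. The SAP's listing of tables assigns both to the per-protocol population.

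**The concern.** The planned total supports the stated 80% power, the 50% interim look and the time at which the database is locked. A reader who takes it from the synopsis gets a different trial size from one who takes it from SAP 8.5.5, and the SAP disagrees with itself (678, 690 and 693).

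Two further questions follow. Does the current figure of 693 deliver the 630 evaluable patients it was built for at the plan's own drop-out rate? And can the final-analysis trigger be met, given that a number which already contains the drop-outs is used to count those who did not drop out?

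**Working it through.** **Inputs (protocol 4.4 and 10.4, repeated in SAP 7 and 8.5.5).** The control failure rate is 20.4%. For the other arm, "we expect the incidence of the primary outcome to be 16.7% in the PCT-guided treatment group". The margin is 5 percentage points, power 80% and allocation 1:1. One-sided alpha is 0.025 before the interim adjustment and 0.0492/2 = 0.0246 after it. Drop-out is 10%.

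**Step 1: reproduce the plan's evaluable numbers.** Unpooled normal approximation for non-inferiority of two proportions:

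n per arm = (z_alpha + z_beta)² × [pC(1 − pC) + pT(1 − pT)] / (margin + pC − pT)²

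- Variance term: 0.204 × 0.796 + 0.167 × 0.833 = 0.162384 + 0.139111 = 0.301495.
- Denominator: (0.05 + 0.037)² = 0.087² = 0.007569.
- Alpha 0.025: (1.9600 + 0.8416)² × 0.301495/0.007569 = 312.6, so 313 per arm and 626 in total, as stated.
- Alpha 0.0246: (1.9668 + 0.8416)² × 0.301495/0.007569 = 314.2, so 315 per arm and 630 in total, as stated.

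The evaluable numbers are therefore right. Any shortfall comes from the drop-out step.

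**Step 2: trace the totals.**

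- 630 × 1.1 = 693 exactly. Retaining 630 after 10% loss needs 630/0.9 = 700.
- 626 × 1.1 = 688.6. Rounding up per arm gives 690 (313 × 1.1 = 344.3, so 345 × 2). The documents do not show this rounding.
- 678 has no derivation. It would follow from 308 per arm, the Table 1 figure (616 × 1.1 = 677.6). That is an inference; 616 appears nowhere.

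**Step 3: loss that 693 allows.** 1 − 630/693 = 9.1%.

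**Step 4: power after 10% loss.** Power = Φ(0.087 / √(0.301495/n) − 1.9668), with n the evaluable number per arm and one-sided alpha 0.0246.

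| Enrolled | Left after 10% loss | n per arm | Power |
|---|---|---|---|
| 678 | 610.2 | 305.1 | 78.8% |
| 690 | 621.0 | 310.5 | 79.5% |
| 693 | 623.7 | 311.85 | 79.7% |
| 700 | 630.0 | 315 | 80.1% |

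The 690 was sized for 626 at one-sided 0.025. On that basis its power after 10% loss is 79.7%.

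**Step 5: the final-analysis trigger.** With 693 enrolled, no replacement and 10% lost, about 624 complete, not 693. Even one loss, or one missing day 10 assessment under the SAP 9.1 definition, leaves the literal condition unmet.

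**Step 6: the interim look.** Half of 678, 690 and 693 is 339, 345 and 346.5 (347), a spread of 8 patients.

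**The case against.** Several points can be made for the plan, and most of them limit the concern.

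- **690 and 693 need not conflict.** A reader might infer that the protocol contradicts itself here. It does not: protocol 4.4 and 10.4 present them as the figures before and after the interim adjustment. What stands is that SAP 7 and 9.1 were left at 690 while SAP 8.1 and 8.5.5 moved to 693. It would also be unfair to test 690 against 630, a requirement it was not built for.
- **The inflation error is small.** It amounts to 7 patients and about 0.4 points of power (80.1% against 79.7%), or 0.3 points below the stated 80%. The deficit of about 3 per arm (315 − 311.85) is no larger than the effect of the variance formula: at alpha 0.0246 a restricted-maximum-likelihood variance gives 317.8 per arm against 314.2 unpooled. The documents do not support reading the trial as underpowered.
- **Not every drop-out is lost to the analysis.** Protocol 8.4 and 8.6 seek the primary endpoint after withdrawal, and SAP 8.4 plans multiple imputation under conditions. Against that, the primary population is per-protocol, and exclusions such as those in SAP 9.3 can reduce it further. The documents give no rate for either, so the evaluable counts are illustrative.
- **The trigger has an obvious benign meaning.** Taken literally, 693 completers at 10% loss would need 693/0.9 = 770 enrolled, and a reader might infer a plan for that many. Nothing supports it: protocol 11.2 includes 693 patients and protocol 8.5 sets a quota of randomised subjects. The likely intent is to wait until those enrolled have passed day 30. The sentence does not say this, and it governs database lock.
- **The 678 in SAP 8.3.1 changes nothing there.** 678/40 = 17.0 years and 693/40 = 17.3 years both exceed 15. The 678 that matters is the one in the synopsis.
- **The interim look is barely affected.** Protocol 10.4 and SAP 8.5.5 set the 50% rule in the same paragraph as 693, and the spread is 8 patients.

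**Conclusion.** The point holds in limited form. The current text carries an underived 678 and, in the SAP, a superseded 690 beside the operative 693. The 693 was obtained by multiplying by 1.1, so it allows 9.1% loss; at the stated 10% it leaves about 624 evaluable and power of about 79.7%, or about 78.8% if 678 were recruited. SAP 8.1 expresses the final-analysis condition as a number of completers that 693 enrolled cannot supply once anyone is lost.

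The power figures rest on the plan's own failure rates, the unpooled normal approximation that reproduces its 313 and 315 per arm, and the assumption that the full 10% leave the analysis. The effect on power is slight, and no conclusion of the trial turns on it. The reason to act is that a stated sample size and a database-lock rule in a confirmatory trial are wrong as written and cheap to correct.

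**What to change.** 1. Replace 678 (protocol synopsis, SAP 8.3.1) and the SAP's 690 (SAP 7 and 9.1) with 693. Protocol 4.4 can keep 690 as its explained intermediate step, and SAP 7 should carry the same explanation if it mentions 690.
2. Beside 693, state either that it allows 9.1% loss or that power is about 79.7% at 10% loss.
3. Reword SAP 8.1 so that the final analysis runs when all randomised patients have completed day 30 or left the study.
4. In the Table 1 and Table 2 shells, remove the conflicting 308 and 315 and leave the per-protocol numbers to be filled from the data. The enrolment total does not belong there.

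Cost: wording only, plus acknowledging power about 0.3 points below 80% at 10% loss. Keeping 693 needs no extra patients; restoring 630 evaluable at 10% loss would need 7 more (700).
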